6.4 Enrolment visit

The enrolment visit will be scheduled as soon as possible, and within a maximum of 3 days after completion of oral metronidazole treatment. This window of 3 days is needed in case the last day of oral metronidazole treatment is in the weekend or during menses. At the enrolment visit, the following procedures will take place:

- 1. Urine pregnancy and urinalysis dipstick testing. If pregnant, not eligible. If UTI, treat and do not yet randomise. Repeat wet mount (and collect Gram stain for Nugent scoring) and enrol based on new wet mount results as in 6.3.2.
- 2. Enrolment informed consent procedures;
- 3. Face-to-face interview (update on current medications, contraception and genital symptoms and baseline assessment of AEs and social harms)
- 4. Speculum examination with collection of vaginal swabs for vaginal pH measurement, wet mount, Gram stain Nugent scoring, TV culture and VMB assessments (see 8.2); endocervical swabs to store for potential NG/CT testing (if required for clinical reasons or for VMB interpretation); and a CVL to store for additional VMB assessments (see 8.2). If BV by Amsel

criteria, TV on wet mount or symptomatic vaginal candidiasis on wet mount, treat and do not yet randomise. Repeat wet mount (and collect Gram stain for Nugent scoring) and enrol based on new wet mount results as in 6.3.2.

- 5. Randomisation;
- 6. HIV/STI/BV risk reduction counselling plus explanation of the intervention that the participant was randomised to (including detailed explanations of potential side effects, and in the case of metronidazole, potential side effects when metronidazole is combined with alcohol use), provision of study products, and application of the first dose of the relevant intervention under supervision of a study staff member (and practice of vaginal self-sampling if in the frequent sampling group). Women will be asked to stay in the study clinic for a minimum of about 30 min after application of the first dose to identify and treat any immediate allergic reactions (these are exceedingly rare).
- 7. Reimbursement, and scheduling of the Day 7 visit;
- 8. Participant leaves the RU clinic;
- 9. Further laboratory testing:
 - Vaginal swabs and CVL: Initial processing and storage of a vaginal Gram stain for Nugent scoring at RU, and vaginal swabs and CVL for VMB and biofilm assessments at UoL (see 8.2);
 - Endocervical swabs: Initial processing and storage for potential local NG/CT testing;

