6.1 Intent-to-treat incidence rates of primary efficacy outcomes

All women at all study visits were tested for BV by Amsel criteria, BV by Nugent scoring, TV by wet mount, TV by InPouch culture and vaginal candidiasis by wet mount.

During follow-up, antibiotic and antifungal treatments were given as follows:

- BV was only treated when a woman had BV by Nugent score or modified Amsel criteria but also reported symptoms typical for BV (unusual vaginal discharge, fishy smell) or these were observed by the study physician during a pelvic examination. A diagnosis could almost always be made on the day of the study visit.
- TV was always treated when identified on wet mount or by TV culture. The wet mount results were always available on the day of the study visit, but the InPouch culture results only 5 days later. If a woman had tested negative by wet mount but positive by InPouch culture, she was asked to return to the RU clinic for treatment.
- Vaginal candidiasis was only treated when Candida was present on the wet mount and the participant reported symptoms that are typical for vaginal candidiasis (itching, curd-like discharge) or these were observed by the study physician during a pelvic examination. A diagnosis could almost always be made on the day of the study visit.

We will describe any antibiotic or antifungal use between randomisation and M2 and between M2 and M6 by indication, drug type and drug dosing schedule.

Each positive case during follow-up will be assessed separately to differentiate between incident infections and persistent infections. We will assess whether treatments were dispensed appropriately and whether participants adhered to the treatments.

The incidence of each primary outcome will be defined as follows:

- Incident BV by modified Amsel criteria: positive by modified Amsel criteria after having been negative by modified Amsel criteria at the previous visit or after a case of symptomatic BV (diagnosed by modified Amsel criteria or by Nugent score) was adequately treated.
- Incident BV by Nugent score 4-10: a Nugent score of 4-10 after a Nugent score of 0-3 at the previous visit or after a case of symptomatic BV (diagnosed by modified Amsel criteria or by Nugent score) was adequately treated.
- Incident BV by Nugent score 7-10: a Nugent score of 7-10 after a Nugent score of 0-6 at the previous visit or after a case of symptomatic BV (diagnosed by modified Amsel criteria or by Nugent score) was adequately treated.

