- UTI: a positive urinalysis result (according to the Rwandan guidelines) at M6 or earlier during follow-up if tested due to symptoms after a negative urinalysis dipstick result at an earlier visit or after adequate UTI treatment. Time at risk will always start at the Enrolment visit because all UTI's at the Screening and Enrolment visits were treated prior to randomisation.
- Pregnancy: a positive urine pregnancy test at M6 (or earlier during follow-up). As being pregnant at Screening or Enrolment was a reason for exclusion in this study, all positive results will be treated as incident cases.

Incidence rates: IRs will be calculated as the number of incident cases per person-days (PD) of follow-up with 95% confidence intervals using the IR function in STATA. IRs will be calculated for each primary endpoint in each of the 4 randomisation groups and for the entire study population. In all cases, IRs will be calculated for the entire follow-up period as described above.

	Group 1		Group 2		Group 3		Group 4		Total	
	n/N ¹	Cases/PD (IR, 95% CI) ²	n/N¹	Cases/PD (IR, 95% CI) ²	n/N¹	Cases/PD (IR, 95% CI) ²	n/N¹	Cases/PD (IR, 95% CI) ²	n/N¹	Cases/PD (IR, 95% CI) ²
HIV										
HSV-2										
Syphilis										
NG										
СТ										
UTI										
Pregnancy										

1. Number of women (n) who developed at least one incident infection during the specified time period as a proportion of the women who completed all follow-up visits in that time period (N).

2. Incident rate (IR): Number of incidence cases per person-days of follow-up, with 95% confidence intervals (CI).

Incidence rate ratios (IRRs) with 95% confidence intervals will be calculated comparing each product use group (groups 2-4) to the control group (group 1) using the IR function in STATA. In addition, IRRs with 95% confidence intervals will be calculated comparing each vaginal probiotic group (group 3 and 4) to the metronidazole group (group 2). As before, these IRRs will be calculated for each primary efficacy outcome for the entire follow-up period.

	Group 2 vs 1 IRR (95% CI)	Group 3 vs 1 IRR (95% CI)	Group 4 vs 1 IRR (95% CI)	Group 3 vs 2 IRR (95% CI)	Group 4 vs 2 IRR (95% CI)
HIV					
HSV-2					
Syphilis					
NG					
СТ					
UTI					
Pregnancy					

The number of incident infections will likely be too small to allow for per-protocol analyses and GEE models as described for the primary efficacy outcomes in 6.3 and 6.4.

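### SAP 8.1 can count one continuing pregnancy, or one UTI that was not adequately treated, as two incident cases

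*SAP*

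**What the plan says.** **UTI (SAP 8.1).** An eligible test is "a positive urinalysis result (according to the Rwandan guidelines) at M6 or earlier during follow-up if tested due to symptoms". It becomes an incident case if it comes "after a negative urinalysis dipstick result at an earlier visit or after adequate UTI treatment". On the start of follow-up the SAP adds: "Time at risk will always start at the Enrolment visit because all UTI's at the Screening and Enrolment visits were treated prior to randomisation". Protocol 6.4 matches this for the Enrolment visit: "If UTI, treat and do not yet randomise".

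**Pregnancy (SAP 8.1).** A positive test at Month 6 or earlier in follow-up counts. Because pregnancy at Screening or Enrolment led to exclusion, "all positive results will be treated as incident cases". No rule ends time at risk at the first positive.

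**Rates (SAP 8.1).** "IRs will be calculated as the number of incident cases per person-days (PD) of follow-up with 95% confidence intervals". The IRRs compare these case-based rates between groups. A separate n/N column is defined as "Number of women (n) who developed at least one incident infection during the specified time period", so it counts each woman once.

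**Comparator (SAP 6.1).** Incident BV by modified Amsel criteria is "positive by modified Amsel criteria after having been negative by modified Amsel criteria at the previous visit", or positive after adequate treatment of symptomatic BV. The Nugent and TV rules have the same structure. Section 6.1 also promises a case-by-case review to separate incident from persistent infections. Section 8.1 does not repeat that review.

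**The concern.** An incidence rate should count episodes. The 6.1 rules for BV and TV do this by looking at the woman's most recent state: she must have been negative at the last visit or been adequately treated. The 8.1 UTI rule accepts a negative from any earlier visit, so once a woman has had one negative dipstick that condition stays met for the rest of follow-up. The pregnancy rule has no condition on the preceding test.

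Where a second eligible test falls within the same episode, the numerator counts tests instead of episodes. Events will be few with 17 women per group, so one duplicated episode can shift an IRR visibly. The duplicate also enters the interval as if it were an independent event.

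**Working it through.** The plan states no event count, rate or IRR for UTI or pregnancy, and SAP 3.1 lists person-time as still to be determined. There is therefore no planned figure to reproduce. The check has three steps.

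**1. Can one episode meet the rule twice?**

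- *Pregnancy.* Women who become pregnant may stay in the study (Protocol 5.4). A pregnancy test is scheduled for everyone at Month 6, with tests at Day 7, Month 1 and Month 2 only when indicated (SAP Table 1 and 8.1). SAP 3.4 also lists a wish for a pregnancy test as a reason for an unscheduled visit. A woman positive before Month 6 and still pregnant at Month 6 has two positives, and both count as worded.
- *UTI.* Every randomised woman was either dipstick-negative at Enrolment or treated before randomisation, so one of the two qualifying conditions holds from the start. Take a woman negative at Enrolment and positive on a symptomatic test at Month 1, whose treatment was not taken or failed. If she is still positive at Month 6, the adequate-treatment condition fails, but the Enrolment negative still qualifies the second positive. Under the 6.1 structure it would not count.
- *HIV, HSV-2, syphilis, NG and CT.* The definitions use the Month 6 result only, so this problem does not arise.

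**2. Direction.** Let q be the repeat positives counted per true episode.

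- Counted rate = true rate × (1 + q). For q = 0.25, 0.5 and 1 the factor is 1.25, 1.5 and 2.
- Counted IRR = true IRR × (1 + q_product) / (1 + q_control).

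| q_product | q_control | IRR factor |
|---|---|---|
| 0.5 | 0.5 | 1.5/1.5 = 1.00 |
| 0.5 | 0 | 1.5/1 = 1.50 |
| 0 | 0.5 | 1/1.5 = 0.67 |

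**3. Illustration.** Assumptions, not in the documents: 182 days per woman, so 17 × 182 = 3,094 person-days per group, and two true episodes in each group. Rate intervals are exact Poisson. IRR intervals are exact conditional binomial with equal person-days.

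| Counted cases, product v control | IRR (95% CI) |
|---|---|
| 2 v 2, one case per episode | 1.00 (0.07 to 13.8) |
| 3 v 2, one product episode counted twice | 1.50 (0.17 to 17.96) |
| 2 v 3, one control episode counted twice | 0.67 (0.06 to 5.82) |
| 4 v 2, both product episodes counted twice | 2.00 (0.29 to 22.1) |
| 2 v 4, both control episodes counted twice | 0.50 (0.05 to 3.49) |
| 4 v 4, all episodes counted twice | 1.00 (0.19 to 5.37) |

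The first and last rows hold the same clinical information, yet the upper limit falls from 13.8 to 5.37. In a group whose two episodes are both counted twice, the rate goes from 2/3,094 = 0.65 per 1,000 person-days (0.08 to 2.34) to 4/3,094 = 1.29 (0.35 to 3.31).

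*Person-time for pregnancy.* Leaving time at risk open works the other way, but weakly. For one pregnancy found at day 60, stopping the clock gives 3,094 − (182 − 60) = 2,972 person-days. The corrected rate is 1/2,972 = 0.34 per 1,000. The literal rule gives 2/3,094 = 0.65. The net factor is 2 × 2,972/3,094 = 1.92.

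**The case against.** Much can fairly be said against giving this point weight.

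- **Few opportunities for repeats.** Month 6 is the only scheduled follow-up dipstick. Earlier dipsticks count only if done for symptoms. A reader might infer that every later positive in an episode becomes a new case, or that one UTI can be counted four times at scheduled visits. The documents do not support that: the visits are scheduled but the dipsticks are not. This stands.
- **UTIs are treated.** Protocol 4.1 says UTIs diagnosed during follow-up will be treated. A positive after adequate treatment is a legitimate new case by the SAP's own logic. This stands, and it confines the UTI problem to treatment that failed, was not taken or was not given.
- **Section 6.1 already reviews persistence.** That review could be extended to UTI and would largely settle the point. But 8.1 does not refer to it, and 6.1 sets it out for the primary outcomes.
- **The pregnancy sentence has another purpose.** It separates incident from prevalent cases, and an analyst would probably count a pregnancy once. The multiple-events rule in 6.1 also speaks of infections. That is a sensible reading of intent, but the words count all positives, and nothing in 8.1 supplies a first-positive rule.
- **Low stakes.** These are secondary outcomes in a pilot, the SAP itself says the sample is too small to test the hypotheses, and the n/N column is unaffected. This stands and limits the importance of the point.

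**Conclusion.** The wording fault is real and modest. As written, a continuing pregnancy detected before Month 6 gives two incident cases while its person-days keep running. A UTI that was not adequately treated can be recounted at a later eligible positive. The pregnancy part is the clearer of the two, because no symptom or treatment condition limits it.

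Repeat counting can only bias case-based rates upward; for pregnancy, the uncut person-time offsets a little of this. A reader might infer that the IRRs are inflated. That does not follow: equal repeats cancel, and repeats in the control group lower the product-versus-control IRR. The IRR is distorted in an unknown direction, and its interval is too narrow whenever repeats are treated as independent events.

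The actual size is unknown and probably small. It needs at least one off-schedule positive followed by another eligible positive in the same episode, and the documents do not show that this happened. The figures above rest on assumed event counts and 182 days of follow-up per woman, and all the intervals are too wide to support different conclusions about any product.

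**What to change.** Change two sentences in SAP 8.1.

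- **UTI:** count an eligible positive only after a negative result at the most recent preceding dipstick, or after documented adequate treatment since the last positive. Keep the adequate-treatment clause. Do not merge consecutive positives merely because no negative lies between them: with no dipstick scheduled between Enrolment and Month 6, that would lose true recurrences after treatment. A cross-reference to the 6.1 review of persistent infections would show how adequacy of treatment is judged.
- **Pregnancy:** count only the first positive test of each pregnancy and end time at risk on that date.

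This needs no new data and brings 8.1 into line with 6.1. The cost is that a UTI that resolved without treatment and without an intervening negative dipstick, followed by a genuinely new UTI, would be counted once.

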3.1 Retention (see also the flow diagram in Figure 1 above)

	N
Number of women who attended a Screening visit	176
Number of women who attended an Enrolment visit	74
Number of women who were randomised	68
Number of women who attended D7, M1, M2, and M6 visits	66, 67, 66, 64
Number of women who completed all scheduled study visits	60
Number of women who missed visits after randomisation	8
Number of women who withdrew early	4
Number of women who were lost-to-follow-up	0
Number of deaths	0
Number of completed study visits by randomised women, including the Enrolment visit	324
Number of skipped visits after randomisation	4
Number of missed visits after randomisation	12
Total person-months of data collected after randomisation	TBD
Total person-days of data collected after randomisation	TBD

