- Incident TV by InPouch culture: a positive TV culture after a negative TV culture at the previous visit, or after a case of TV (diagnosed on wet mount or by InPouch culture) was adequately treated.
- Symptomatic vaginal candidiasis: Candida on wet mount plus the presence of symptoms (which the study physician deemed eligible for treatment) after a negative wet mount at the previous visit, a positive wet mount at the previous visit but in the absence of treatment (i.e.no treatment was given), or after adequate treatment for symptomatic vaginal candidiasis.
- In all definitions, one woman can have multiple incident infections, and all of these will be included in incidence rate (IR) and incidence rate ratio (IRR) calculations.

Incidence rates: IRs will be calculated as the number of incident cases per person-days (PD) of follow-up with 95% confidence intervals using the IR function in STATA. IRs will be calculated for each primary endpoint in each of the 4 randomisation groups and for the entire study population. IRs will be calculated for three time periods: between the Enrolment visit and the M2 visit (during product use), between the M2

visit and M6 visit (after cessation of product use) and for the entire study period after randomisation. They will be reported in the following table (one table for each time period):

	Gr	oup 1	Gr	oup 2	Gr	oup 3	Gr	oup 4	Т	otal
	n/N ¹	Cases/PD (IR, 95% CI) ²	n/N¹	Cases/PD (IR, 95% CI) ²						
Incident BV by modified Amsel criteria										
Incident Nugent 4-10										
Incident Nugent 7-10										
Incident TV by culture										
Incident symptomatic vaginal candidiasis										

1. Number of women (n) who developed at least one incident infection during the specified time period as a proportion of the women who had at least one follow-up visit in that time period (N).

2. Incident rate (IR): Number of incidence cases per person-day of follow-up, with 95% confidence intervals (CI).

The median Nugent score and vaginal pH category at each study visit for each study group and the total study population will be visualised using line graphs as follows:

- Nugent score as a count between 0 and 10 (median for the group)
- Vaginal pH as the ordinal categories on the pH strip (median category for the group)

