8.1 Incidence and incidence rate ratios of secondary efficacy outcomes

It has been hypothesised that a lactobacilli-dominated VMB would protect women from HIV, other STIs, and UTIs, and would facilitate pregnancy. While the sample size of this study was too small to adequately test these hypotheses, we did include incidence of HIV, STIs (other than TV), UTIs, and pregnancy as secondary outcomes. Women were tested for HIV and STIs (HSV-2, syphilis, CT, and NG) at the Screening and M6 visits, and for UTI and pregnancy at the Screening, Enrolment and M6 visits. In all cases, additional testing may have been done at the D7, M1 and M2 visits when clinically indicated. Incidence of these secondary outcomes will be determined between baseline (using endpoint data from the Enrolment visit if available and otherwise from the Screening visit) and M6.

Incident cases will be defined as follows:

- HIV: a positive result for the HIV serology algorithm at M6. Women who were HIV-positive at Screening were excluded from the study; therefore, all positive results at M6 will be treated as incident cases. Time at risk will start at the Enrolment visit.
- HSV-2: a positive result for HSV-2 serology at M6. Only those participants who tested negative for HSV-2 at Screening were retested at M6; therefore, all positive cases at M6 will be treated as incident cases. Time at risk will start at the Enrolment visit.
- Syphilis: a positive result for the syphilis serology algorithm at M6. All participants positive for syphilis at Screening were adequately treated prior to randomisation; therefore, all positive cases at M6 will be treated as incident cases. Time at risk will start at the Enrolment visit.
- NG: a positive result for NG PCR at M6 after a negative NG PCR result at Screening (time at risk will start at the Enrolment visit) or after having been successfully treated for NG during follow-up (time at risk will start on the treatment completion date).
- CT: a positive result for CT PCR at M6 after a negative CT PCR result at Screening (time at risk will start at the Enrolment visit) or after having been successfully treated for CT during follow-up (time at risk will start on the treatment completion date).

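### SAP 8.1 applies one all-visits denominator to every secondary outcome, leaving out 4 women seen at Month 6 and counting HSV-2-seropositive women who cannot become cases

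*SAP*

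**What the plan says.** Footnote 1 to the incidence table in SAP 8.1 defines n as women with at least one incident infection, reported "as a proportion of the women who completed all follow-up visits in that time period (N"). The same footnote serves all seven rows: HIV, HSV-2, syphilis, NG, CT, UTI and pregnancy. There is only one period: "In all cases, IRs will be calculated for the entire follow-up period as described above". A woman therefore has to attend Day 7, Month 1, Month 2 and Month 6 to be in N.

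The case definitions in SAP 8.1 do not need all four visits. HIV, syphilis, HSV-2, NG and CT are defined on the M6 result. UTI and pregnancy may also be detected earlier in follow-up. For HSV-2, "Only those participants who tested negative for HSV-2 at Screening were retested at M6". Protocol 6.3 makes a positive HSV-2 result irrelevant to eligibility, so seropositive women could be randomised. For NG and CT, a woman positive at Screening becomes at risk only once she has been successfully treated.

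The matching footnote for the primary outcomes (SAP 6.1) follows a different rule: n is reported "as a proportion of the women who had at least one follow-up visit in that time period (N"). No reason for the difference is given.

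**The concern.** A denominator for an incidence proportion should hold the women who could have become cases and whose status is known. Footnote 1 departs from this in both directions. It removes women who reached M6 but skipped an earlier visit, although the earlier visit is not needed to determine the five M6-defined outcomes. It keeps women who were HSV-2 seropositive at Screening, who under the retesting rule can never appear in n. It is also silent on NG and CT, where the text above the table does treat baseline infection as affecting time at risk.

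The stake is the accuracy of the reported proportions, above all for HSV-2. According to the protocol's rationale, this pilot is meant to inform the design of a later efficacy trial, so proportions taken forward from it should rest on women at risk.

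**Working it through.** **Inputs from SAP 3.1**
- Randomised: 68 women
- Seen at Day 7, Month 1, Month 2 and Month 6: 66, 67, 66 and 64 women respectively
- Every visit made (the row headed "Number of women who completed all scheduled study visits"): 60 women
- One or more visits missed: 8 women
- Early withdrawals 4; nobody lost to follow-up; no deaths

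**Step 1: reproduce the footnote's N.** 68 − 8 = 60, which agrees with the stated 60. M6 attendance: 68 − 4 = 64, which agrees with the stated 64.

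The visit totals in the same table do not fully reconcile. Attendance gives 68 + 66 + 67 + 66 + 64 = 331 visits and 4 × 68 − 263 = 9 missed visits, against 324 and 12 stated. This does not touch the two counts used here, each of which is confirmed separately above.

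**Step 2: women left out.** Everyone who completed all visits attended M6, so 64 − 60 = 4 women attended M6 but fall outside N (4/64 = 6.25%). Assuming every M6 attendee was tested:

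| Cases | Out of 60 | Out of 64 |
|---|---|---|
| 1 | 1.67% | 1.56% |
| 3 | 5.00% | 4.69% |

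**Step 3: HSV-2.** Let p be the proportion seropositive at Screening. The HSV-2 rows in SAP 4.1 and 4.2 are blank table shells, so p is an assumption. Women at risk with an M6 result = 64 × (1 − p). For a fixed number of cases, the understatement from dividing by 60 is 1 − 64(1 − p)/60.

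| Assumed p | At risk | Understatement against N = 60 | 3 illustrative cases: n/60 | 3 cases among women at risk |
|---|---|---|---|---|
| 30% | 44.8 | 25% | 5.0% | 6.7% |
| 50% | 32.0 | 47% | 5.0% | 9.4% |
| 70% | 19.2 | 68% | 5.0% | 15.6% |

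**Step 4: NG and CT.** SAP 6.3 reports women randomised with a CT or NG infection as 8/17, 7/17, 4/17 and 7/17, that is 8 + 7 + 4 + 7 = 26 of 68. The two infections are combined and some women will have become at risk after treatment, so 26 is not the number to remove from either row. It shows that baseline infection was common and that the count varied from 4 to 8 of 17 between arms.

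**Step 5: rates.** SAP 8.1 builds incidence rates and rate ratios on person-days, so leaving 4 women out of N changes neither. If seropositive women's days were counted for HSV-2, each arm's rate would be multiplied by about (1 − p) for that arm. The rate ratio would be multiplied by (1 − p in the product arm)/(1 − p in the control arm), which differs from 1 only if prevalence differs between arms.

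**The case against.** The strongest reply is that n/N is a descriptive column with no test or between-arm comparison attached. The comparisons are rate ratios on person-days, and SAP 8.1 speaks of time at risk for each infection. A seropositive woman has no time at risk for HSV-2, and the NG and CT definitions start the clock at treatment completion where needed. This stands. A reader might infer that the rates are diluted, or that unequal HSV-2 status between arms would pass for a product effect. The documents do not establish either. Both depend on seropositive women's days being counted, which the SAP neither states nor explicitly excludes.

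A reader might also infer that n is not a subset of N, for example because of a positive result in one of the 4 women, or a UTI found before withdrawal. That is one reading. The footnote can equally mean that n is counted among women who completed all visits, and no document shows a case outside N. On that second reading the cost is different: any case among the 4 women goes unreported.

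Nor should the HSV-2 understatement simply be equated with the prevalence. That holds when both denominators come from the same set of women. Against the footnote's 60, with the same cases, it is 25%, 47% or 68%.

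Finally, SAP 4.2 tabulates HSV-2 status at Screening by arm, so a careful reader could see roughly how many women were at risk. This reduces the harm but does not correct the reported proportion.

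**Conclusion.** The footnote's denominator is wrong for the n/N column if applied as written. For the M6-defined outcomes it uses 60 women where 64 attended M6, and the effect on any proportion is small. For HSV-2 it includes women who cannot become cases. The size depends on a prevalence that the documents do not give, and the figures above also assume that every M6 attendee has a result and that prevalence among them equals the assumed p. For NG and CT the same at-risk gap exists, but its size cannot be derived from the combined counts.

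Severity is modest. These are descriptive secondary outcomes in a pilot that SAP 8.1 itself calls too small to test the hypotheses behind them.

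**What to change.** Replace footnote 1 in SAP 8.1 with a denominator for each row, count n within that N, and show N in every row:

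- **HIV and syphilis:** women with an M6 result.
- **HSV-2:** women negative at Screening with an M6 result. State that HSV-2 person-days cover only these women.
- **NG and CT, separately:** women with an M6 result who were negative for that infection at Screening or were successfully treated for it during follow-up.
- **UTI and pregnancy:** all randomised women with at least one follow-up visit, the rule already used in SAP 6.1. Do not select these women by whether a test was done. SAP 8.1 says that testing at Day 7, Month 1 and Month 2 was done when clinically indicated, so a test-based rule would admit a woman who withdrew early because she had symptoms and omit one who withdrew well.

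The cost is a change of footnote and the row-specific counts; no new data are needed. The downside is that denominators differ between rows, so proportions can no longer be read down the column against a single N.
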